1.2 BACKGROUND ON RO7234292

Neuropathological abnormalities in HD appear to be the consequence of a toxic gain-of-function of the mHTT protein (Wexler et al. 1987; Walker 2007; Moumné et al. 2013). Therefore, a therapy that reduces synthesis of the toxic mHTT protein should directly target the primary disease mechanism. As the genetic origin of HD is localized to a single gene, inhibiting the expression of this HTT gene is a promising therapeutic option (Stanek et al. 2013).

RO7234292 (RG6042) was originally developed by Ionis Pharmaceuticals, Inc. and was formerly known as ISIS443139 and IONIS-HTTRx. This antisense oligonucleotide (ASO) was developed to reduce the synthesis of all forms of the HTT protein by targeting the HTT messenger ribonucleic acid (mRNA) from both the wild-type and the mutant alleles and directing its catalytic degradation through the action of ribonuclease H1, an endogenous enzyme present in most mammalian cells (Crooke and Bennett 1996; Cerritelli and Crouch 2009), including cells of interest in the central nervous system (CNS) (e.g., neurons and neuroglia). Reduction of the HTT gene mRNA, which in turn

limits translation of the wild-type and mutant huntingtin protein, could potentially inhibit all downstream toxic effects and lead to a sustained reversal in HD symptoms.

Pharmacology data support selective targeting of HTT mRNA transcripts from both alleles as a potentially safe and effective mechanism for the treatment of HD. Using ASOs targeting human HTT mRNA in rodents and non-human primates, significant reduction of mHTT mRNA transcripts, wild-type HTT mRNA transcripts, and mHTT protein has been achieved throughout most brain regions (Kordasiewicz et al. 2012). Furthermore, transient delivery of these ASOs in transgenic mouse models of HD delayed disease progression and mediated a sustained reversal of disease phenotype that persisted longer than HTT mRNA knockdown (Kordasiewicz et al. 2012; Stanek et al. 2013).

Non-clinical proof-of-concept studies with ASOs targeting mHTT have been conducted in 3 models of HD, including YAC128 mice expressing the full-length mutant human HTT transgene with a 128 CAG repeat expansion, BACHD mice expressing the full-length human mHTT genomic sequence with 97 CAG/CAA repeats, and R6/2 mice expressing exon 1 of the human mHTT gene with 110 to 135 CAG repeats. These studies demonstrate that ASOs targeting human HTT mRNA improve motor function and protect against human HTT transgene expression in YAC128 mice; improve motor function, hypoactivity, and stress response in BACHD mice; and preserve striatal volume and increase survival in R6/2 mice.

The pharmacokinetics (PK) and toxicity of intrathecal (IT) administration of RO7234292, an ASO that targets human HTT mRNA, were assessed in cynomolgus monkeys for 13 weeks (biweekly for the first month, then monthly thereafter) at dose levels up to 50 mg/dose (5 bolus administrations, for a total dose of 250 mg) and chronically for 9 months, up to 35 mg/dose (10 bolus monthly administrations for a total dose of 350 mg). The drug was safe and well tolerated in these studies.

In a first-in-human, Phase I/IIa double-blind, placebo-controlled, dose-escalation study (Clinicaltrials.gov Identifier NCT02519036) (ISIS 443139-CS1) four doses of RO7234292 (ranging from 10 to 120 mg) were well tolerated and achieved significant dose-dependent lowering of cerebrospinal fluid (CSF) mHTT protein when administered IT every 4 weeks to 46 patients with early manifest HD. Exploratory analyses identified a relationship between lowering of mHTT protein and improvement in some clinical measures. Taken together, these data support further clinical testing to demonstrate definitive clinical benefit of mHTT protein reduction in the CNS. The data from this study also supported the initiation of Study ISIS 443139-CS2 (Study BN40697; Clinicaltrials.gov Identifier NCT03342053), a Phase II open-label extension (OLE) study for patients who participated in Study ISIS 443139-CS1. This on-going open-label study is evaluating the longer-term safety and tolerability of RO7234292 and the sustained effect of the drug on lowering CSF mHTT protein of both a monthly and bimonthly (i.e., every other month) regimen.

Nine-month clinical data from the ongoing, 15-month, Phase II OLE Study BN40697 including CSF mHTT protein, exploratory fluid biomarkers, and safety/tolerability data are available for reporting. All individuals in Study BN40967 have reached the 9-month timepoint of the planned 15-month study, and several individuals have now received RO7234292 for over 1 year on both regimens. Study BN40697 will be continued until its anticipated completion by December 2019. Preliminary data show that a 120 mg every-8-weeks (Q8W; every 2 months) dosing regimen of RO7234292 achieves 47% median CSF mHTT lowering at trough (i.e., sample taken immediately before the next dose) and the 120 mg every-4-weeks (Q4W) dosing regimen achieves 66% median lowering at trough. Both results exceed the 20% to 40% target for CSF mHTT lowering at trough and steady state based upon efficacy data from nonclinical models, and exceed the result of approximately 40% median lowering observed in the completed Phase I/IIa study.

Further details on non-clinical and clinical studies can be found in the RO7234292 Investigator's Brochure.

1.3 STUDY RATIONALE AND BENEFIT-RISK ASSESSMENT

Presently, there are no therapies available to stop or slow the clinical progression of HD, which is relentless until patients experience premature death. The ASO RO7234292 is designed to target the cause of HD and offers the potential to meet this unmet medical need.

To date, non-clinical and clinical data have been generated to support further investigation of RO7234292 in patients with early manifest HD.

Building on the completed Phase I/IIa study and the ongoing OLE Study BN40697, this Phase I study (BP40410) will collect clinical PK and pharmacodynamics (PD) data to characterize the magnitude and duration of CSF mHTT reduction after short-term IT bolus dosing with RO7234292. This study will also further inform the semi-mechanistic population PK/PD model that has been developed on the basis of the currently available clinical and non-clinical data. Ultimately, this will guide clinical decision-making about optimal treatment regimens by providing information about the relationship between RO7234292 dosing and the time course of mHTT reduction, which could not be obtained any other way.

This study is open-label and will be conducted in an early manifest HD population over 8 months including an approximately 4-week screening period and an approximately 28-week study period.

Patients will be admitted to the site in the afternoon/evening of Day -2 or in the morning of Day -1 to begin the first in-house period of the study. After completing the safety assessments *including Holter ECG*, an IT catheter will be inserted *on the morning of Day 1* to facilitate frequent CSF sampling and IT bolus dosing of RO7234292. After

baseline CSF sampling, a single dose of RO7234292 will be given, after which sampling will continue for a further 48 hours before the catheter is removed. The patients will be discharged on Day 4 after all assessments have been completed.

Patients will return to the site for the second in-house period in the afternoon/evening of Day 28 or in the morning on Day 29 and will be discharged on Day 29 after all assessments have been completed. The second dose of RO7234292 will occur via a lumbar puncture on Day 29.

Patients will return to the site for daily visits on Days 30, 43, 71, 127, and the follow-up visit (6 months after the last study drug administration).

After study completion, participants will be eligible to enroll in an OLE study (Study BN40955) with active RO7234292 compound, provided the data from the ongoing RO7234292 program support continued development, the patient meets the inclusion and exclusion criteria for the OLE, and the OLE is approved by the relevant competent authorities and Ethics Committees (ECs).

The known potential risks associated with RO7234292, as well as additional study associated risks related to lumbar IT study drug administration, are elaborated in the Guidance to Investigator section of the Investigator's Brochure and Section 5.1 of this protocol.

The patients participating in this study are not expected to benefit given only two doses will be administered; appropriate measures have been taken to minimize risks. The study will provide critical data for RO7234292 to potentially enable patients with HD to benefit from treatment in the future.

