- Magnetic resonance imaging (MRI) has been added as an assessment during the screening period and at the follow-up visit 6 months after the last study drug administration (or at early termination visit, if applicable). MRI is a non-invasive method to assess structure and function of the human brain and can provide insights into the pathophysiological mechanisms of neurologic and neuropsychiatric diseases. Standard safety sequences will be acquired; structural MRI will be used to assess brain volume. If clinically indicated, optional diffusion-weighted and resting state functional MRI sequences will be acquired. MRI assessments will primarily serve as a safety measure to exclude any contraindication to IT catheter insertion and lumbar puncture and any overall contraindication to participation in Study BP40410. In addition, both screening and 6-month follow-up MRI assessments will serve as a baseline assessment to enable ongoing safety monitoring for those patients who enroll in the open-label extension study (OLE) Study BN40955 upon completion of Study BP40410.
- The dose level used for enrolled patients in the third dose group has been modified from 90 mg to 30 mg. This change will potentially enable a reduction in the total number of patients to be recruited and to undergo IT catheter insertion, as relevant data will be collected from the first 12 patients (as originally planned). Data generated in recently completed Phase I/Ia Study (ISIS 443139-CS1) and ongoing OLE Study BN40697 have enabled refinement of model-based simulations, leading to the indication that 30 mg doses of RO723429 may be more informative than 90 mg doses to enable characterization of the pharmacokinetics, pharmacodynamics, and pharmacokinetic/pharmacodynamic relationships of RO723429, i.e. addressing the primary study objectives.
- Safety Section 5.1 has been updated with recent data from the 15-month data analysis of the ongoing OLE Study BN40697.

Changes to the protocol are summarized below:

- Because duration of the catheter presence is believed to be one of the risk factors for infection, the indwelling IT-catheter duration has been reduced from 96 hours to 48 hours by eliminating the insertion 24 hours predose and the final day of sampling postdose. Thus, the catheter will be inserted prior to dosing on Day 1 and will be removed 48 hours after dosing. Applicable changes have been made to Section 1.3, Figure 1 and the schedules of activities (Appendix 1 and Appendix 2).

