4.5.5 Collection of Cerebrospinal Fluid (Lumbar Puncture Procedure)

*Skin (groin area) and nose swabs will be taken during screening to test for Methicillin-resistant *Staphylococcus aureus* (MRSA). If the MRSA screening result is positive, treatment for decolonization (as per local standard procedure) should be administered for 5 days prior to catheter insertion.*

In preparation for the catheter insertion, patients will be required to remove all body piercings, make up, and nail polish and to cleanse the entire body (including hair) with antibacterial soap on Day -2 or Day -1.

Within 72 hours prior to performing each scheduled lumbar puncture or IT catheter insertion, local laboratory analysis of coagulation factors (international normalized ratio [INR], activated partial thromboplastin time [aPTT], prothrombin time [PT]) and platelets must be conducted and the results reviewed. Each lumbar puncture should be performed at approximately the same time at each visit (ideally in the morning between 8:00 a.m. and 12:00 noon or in the early afternoon between 12:00 noon and 3:00 p.m.) to minimize potential diurnal variation of CSF parameters. *A 20 mL sample will be taken at predose after the IT catheter has been inserted. Subsequently, during the CSF sampling period until 48 hours postdose, a maximum 5 mL of CSF fluid will be collected (via the IT catheter) at each timepoint indicated in [Appendix 2](#). In addition, up to 2 mL CSF sample will be collected for daily CSF safety testing, including culture, during the indwelling-catheter period at the timepoints indicated in [Appendix 1](#) and [Appendix 2](#). Upon removal, the catheter tip should be sent for culture.*

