5.1.1.4 Known Risks Associated with an Indwelling Catheter

Insertion of an intrathecal catheter carries the same risks as a lumbar puncture, with additional risks of catheter blockage, disconnection or retraction.

Of note, in the current study, 2 out of 6 patients developed a lumbar abscess after having had the catheter implanted for 4 days.

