Elevations in CSF WBC count or proteins or suspected meningitis, radiculitis, arachnoiditis, hydrocephalus , or other acute neurologic symptoms	
 Withhold study drug if diagnosis of meningitis, radiculitis, arachnoiditis, hydrocephalus or acute neurologic symptoms is suspected and initiate appropriate diagnostic work-up as indicated. Clinical signs and symptoms of hydrocephalus (e.g. new onset of persistent or worsening gait disturbance, change in level consciousness/ cognition, changes in continence, or a combination of all three signs) are required for diagnosis of suspected hydrocephalus. Clinical signs and symptoms of meningitis (e.g., headache, stiff neck, and fever) plus confirmatory WBC count are required for diagnosis of suspected meningitis and clinical signs and symptoms are required for diagnosis of radiculitis, arachnoiditis or acute neurologic symptoms. Isolated low-level (e.g., 5 to 50/μL WBC count) elevations in CSF WBC count without clinical symptoms do not meet criteria for diagnosis of suspected meningitis. In the event of persistent back pain or fever, promptly consider imaging investigation to exclude spinal abscess and discuss with Medical Monitor. The Medical Monitor should be consulted in all cases of WBC count CSF elevations, or a change from baseline in CSF proteins greater than twice baseline, or where there is uncertainty to discuss next steps of patient management in the study. If a diagnosis of suspected meningitis, radiculitis, arachnoiditis, hydrocephalus or acute neurologic symptoms is refuted, the study drug may be resumed after consultation with the Medical Monitor. In the event meningitis, radiculitis, arachnoiditis, hydrocephalus or acute neurologic symptom diagnosis is confirmed, standard-of-care therapies should be instituted as indicated.

ALT=alanine aminotransferase; AST=aspartate aminotransferase; CrCl=creatinine clearance; CSF=cerebrospinal fluid; eGFR=estimated glomerular filtration rate; INR=international normalized ratio; ULN=upper limit of normal; WBC=white blood cell.

Table 1 Guidelines for Management of Patients Who Experience Adverse Events (cont.)

Event	Action to Be Taken

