5.3.1 Adverse Event Reporting Period

Investigators will seek information on adverse events at each patient contact. All adverse events, whether reported by the patient or noted by study personnel, will be recorded in the patient's medical record and on the Adverse Event eCRF.

After informed consent has been obtained but prior to initiation of study drug, all adverse events caused by a protocol-mandated intervention (e.g., invasive procedures such as catheter insertion, biopsies, discontinuation of medications) should be reported. If the adverse event meets the criteria for serious adverse event, it should be reported immediately (see Section 5.4.2 for instructions for reporting serious adverse events).

After initiation of study drug, all adverse events will be reported until the follow-up visit or until the patient receives his or her first dose of study drug in the OLE study (Study BN40955), at which time reporting will occur per the new study requirements.

Instructions for reporting adverse events that occur after the adverse event reporting period are provided in Section 5.6.

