5.3.2 Eliciting Adverse Event Information

A consistent methodology of non-directive questioning should be adopted for eliciting adverse event information at all patient evaluation timepoints. Examples of non-directive questions include the following:

"How have you felt since your last clinic visit?"

"Have you had any new or changed health problems since you were last here?"

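### After two lumbar abscesses in six catheterized patients, the protocol schedules no contact between discharge on Day 4 and Day 28; at least one safety call should be added

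*Protocol*

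**What the plan says.** Section 5.1.1.4 of the protocol records that in this study "2 out of 6 patients developed a lumbar abscess after having had the catheter implanted for 4 days". The amendment rationale says that "the indwelling IT-catheter duration has been reduced from 96 hours to 48 hours", and Section 1.3 confirms the current schedule: insertion on the morning of Day 1 and removal 48 hours after dosing, which is Day 3.

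Version 4 also adds infection precautions and tests (Sections 4.5.5 and 4.5.6): MRSA swabs, antibacterial washing, CRP, ESR, local hematology and daily CSF safety samples with culture while the catheter is in place. At the end, "Upon removal, the catheter tip should be sent for culture". Section 5.1 gives quicker recognition of catheter-related infection as one aim of these measures.

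On what follows, Section 1.3 says "The patients will be discharged on Day 4 after all assessments have been completed" and then "Patients will return to the site for the second in-house period in the afternoon/evening of Day 28", or on the morning of Day 29. Figure 1 and Appendix 1 go directly from Day 4 to Day 28.

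Three provisions bear on the interval between. Table 1 (Section 5.1.3.3) says "In the event of persistent back pain or fever, promptly consider imaging investigation to exclude spinal abscess". Section 5.3.1 says "Investigators will seek information on adverse events at each patient contact". Section 5.5.1 has the investigator follow recorded events to resolution or stability.

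**The concern.** The catheter comes out on Day 3, the patient goes home on Day 4, and the plan then schedules nothing until the admission for the second dose. Table 1's imaging step can start only once the site knows of back pain or fever, and adverse events are sought at contacts, of which none is scheduled on Days 5 to 27. A symptom that begins after discharge reaches the site only if someone reports it.

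Unprompted reporting is not a strong sole safeguard in this population. Section 1.1 describes progressive cognitive decline in the disease, and Section 4.1.1 requires a study companion only where one is available. Lumbar abscess is a serious harm already seen in this study, in patients whom Section 1.3 does not expect to benefit. What is at stake is the time to recognition of a known procedural complication.

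**Working it through.** The plan states no figure for this interval and no formal statistical basis for its sample size (Section 6.1), so there is nothing to reproduce. The check takes differences between scheduled days.

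**Inputs.** Catheter removal on Day 3, discharge on Day 4, next admission on Day 28 or the morning of Day 29 (Section 1.3). Window of ±2 days at Days 28 and 29 (Appendix 1). CRP and ESR on Day 4 and next on Day 29 (Appendix 1). Plasma PK sampling goes from Day 4 to Day 28 (Appendix 1, footnote u).

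**Length of the gap.**
- Discharge to next contact: 28 − 4 = 24 days; with the window, 26 − 4 = 22 to 30 − 4 = 26.
- Arrival on the morning of Day 29: 29 − 4 = 25 days.
- Catheter removal to next contact: 28 − 3 = 25 days.
- CRP/ESR: 29 − 4 = 25 days; with the window, 27 − 4 = 23 to 31 − 4 = 27.

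**Routes by which the site could learn of an abscess on Days 5 to 27.**
- A CSF or catheter-tip culture that reports after discharge. Section 5.3.5.5 makes the investigator responsible for reviewing laboratory findings, so this route needs no symptom report.
- An unprompted report by the patient or companion.
- Follow-up of an event already recorded by Day 4 (Section 5.5.1).

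None of these is a scheduled inquiry about symptoms that start after discharge. The mobile app in Section 4.5.8.8 is mentioned only for a cognitive test.

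**Effect of calls.** The longest contact-free interval is the largest difference between successive contacts from Day 4 to Day 28. Call days are examples, since the documents propose none.

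| Calls | Intervals (days) | Longest | Longest if admission slips to Day 30 |
|---|---|---|---|
| None | 24 | 24 | 26 |
| Day 10 | 6, 18 | 18 | 20 |
| Day 16 | 12, 12 | 12 | 14 |
| Days 10 and 19 | 6, 9, 9 | 9 | 11 |

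Day 16 is the best single call on this measure. An earlier call could be better if abscesses tend to appear early, which the documents do not show.

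**What the event count supports.** 2/6 = 33.3%. The Clopper-Pearson 95% interval runs from the 0.025 quantile of Beta(2, 5) to the 0.975 quantile of Beta(3, 4): 4.3% to 77.7%. This describes the 4-day catheter and does not estimate the rate at 48 hours.

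**Patients still to be dosed.** If the six patients count toward the planned 12 or the maximum of 20, 12 − 6 = 6 or 20 − 6 = 14 remain. That is 6 to 14 calls with one each, or 12 to 28 with two.

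**The case against.** The strongest reply is that need has not been shown. The two abscesses arose under a catheter duration no longer used. Version 4 responded with a shorter duration and a set of infection tests, and the cultures can raise an alarm after discharge without any symptom. Table 1 gives specific guidance. SAP Section 4.7 provides for listing unscheduled visits, so assessment outside the schedule is foreseen. Enrolled patients walk unassisted, have an Independence Scale score of at least 70 and are judged able to comply, so many would presumably call. Consent pages were removed before this review, and the lumbar puncture manual and Safety Management Plan were not supplied; any of these may contain reporting instructions.

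Much of this stands. The culture route is real, and silence in these two documents does not show that patients go home uninstructed. But a negative culture or an instruction sheet does not ask a patient about back pain in the second or third week. Section 4.5's general commitment to monitoring creates no contact. Its pre-dose check guards the second dose without bringing recognition forward.

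A second objection is that new contacts disturb the safety comparison. It is correct, and wider than prompted questions: even an open question at an added call gives later patients an extra chance to report events. Dose follows enrollment order (Section 3.1). If the six were the first enrolled, four had 120 mg and two had 60 mg, so the extra ascertainment would begin partway through the 60 mg group. The fix must allow for this.

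**Conclusion.** The point holds as a cheap improvement to patient safety. No contact is scheduled for 24 days (22 to 26 with the window) after discharge from a catheter period in which two of six patients, under the longer duration, developed a lumbar abscess.

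Three stronger readings are tempting and unsupported.
- A reader might infer that either abscess was found late. The documents give no onset or detection dates.
- A reader might infer that Version 4 neglected the infection risk. It did not: duration was halved and several tests were added.
- A reader might turn the shorter intervals into a percentage reduction in time to diagnosis. That would require the distribution of onset, the share of patients who would stay silent, and the sensitivity of a call. None is given, so the benefit is stated only as the longest contact-free interval: 24 days now, 18 with a call on Day 10, 12 with one on Day 16, 9 with calls on Days 10 and 19.

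Later gaps are longer (28 days from Day 43 to Day 71, 56 from Day 71 to Day 127), but they do not directly follow an indwelling catheter. Whether one call suffices is a clinical judgment that depends on the two onset dates.

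**What to change.** Add to Appendix 1 at least one safety telephone call by existing site staff between Day 4 and Day 28. The sponsor should set number and timing from the onset dates of the two cases. Cross-refer from Sections 4.5.5, 5.1 and 5.3.2.

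Each call opens with the open adverse event question, since Section 5.3.2 asks that "A consistent methodology of non-directive questioning should be adopted for eliciting adverse event information at all patient evaluation timepoints". It then asks separately about back pain, fever, headache, stiff neck and new neurologic symptoms. A positive answer leads to an unscheduled assessment under Table 1.

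Flag every adverse event first reported at a call, prompted or not, and show incidence by dose level with and without these events. SAP Section 4.7.2 already allows selected events, such as procedure-related ones, to be tabulated separately, but it defines no such flag, so this is an added output.

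The cost is a protocol amendment with ethics committee and, where locally required, regulatory approval (Section 9.6), possible consent revision and re-consent (Section 8.2), a call script, an eCRF field, one output, and one or two calls for each of the 6 to 14 remaining patients (on the counting assumption above). No sample or procedure is added. A call neither lowers the infection risk nor replaces an examination or CRP/ESR.
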